10.1.4 Serious Adverse Events/Drug Reaction

A serious adverse event (SAE) is any untoward medical occurrence that at any dose:

- Results in death.
- Is life-threatening.

NOTE: The term "life-threatening" in the definition of "serious" refers to an event in which the subject was at risk of death at the time of the event; it does not refer to an event which hypothetically might have caused death if it were more severe.

- Requires inpatient hospitalization or prolongation of existing hospitalization. NOTE: Inpatient hospitalization is defined as 24 hours in a hospital or an overnight stay. An elective hospital admission to treat a condition present before exposure to the study drug, or a hospital admission for a diagnostic evaluation of an AE, does not qualify the condition or event as an SAE. Further, an overnight stay in the hospital that is only due to transportation, organization, or accommodation problems and without medical background does not need to be considered an SAE.
- Results in persistent or significant disability/incapacity.
- Is a congenital anomaly.

NOTE: A congenital anomaly in an infant born to a mother who was exposed to the study drug during pregnancy is an SAE. However, a newly diagnosed pregnancy in a subject who has received a study drug is not considered an SAE unless it is suspected that the study drug(s) interacted with a contraceptive method and led to the pregnancy.

• Is an important medical event.

NOTE: Medical and scientific judgment should be exercised in deciding whether it is appropriate to consider other situations serious, such as important medical events that may not be immediately life-threatening or result in death or hospitalization but may jeopardize the subject or may require intervention to prevent 1 of the other outcomes listed in the definition above. Examples of such events are intensive treatment in an emergency room or at home for allergic bronchospasm, blood dyscrasias or convulsions that do not result in hospitalization, or development of drug dependency or drug abuse. The occurrence of malignant tumors is also to be considered serious.

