10.2.6.3 Nonserious Adverse Events

Axsome will review nonserious AEs that are recorded in the CRFs on a regular basis.

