11. DATA SAFETY MONITORING BOARD

No Data Safety Monitoring Board will be convened during the study.

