AEs will be summarized by the number and percent of subjects in each primary SOC and preferred term. Patients will be counted only once for each primary SOC and each preferred term. Summary tables of AEs by primary SOC, preferred term and severity will be provided. If a subject has more than one AE coded to the same preferred term, the subject will be counted only once for that preferred term by using the event with the highest severity. Similarly, if a subject has more than one AE within a primary SOC category, the subject will be counted only once in that SOC category by using the event with the highest severity. AEs by primary SOC, preferred term and relationship to study drug will be provided as well. If a subject has more than one AE coded to the same preferred term, the subject will be counted only once for that preferred term by using the most related event. Similarly, if a subject has more than one AE within a primary SOC category, the subject will be counted only once in that primary SOC category by using the most related event. Similarly, if a subject has more than one AE within a primary SOC category, the subject will be counted only once in that primary SOC category by using the most related event. Similarly, if a subject has more than one AE within a primary SOC category, the subject will be counted only once in that primary SOC category by using the most related event. In addition, serious adverse events (SAE) by primary SOC and preferred term will be provided. Deaths and SAEs will be summarized similarly to AEs. All adverse event tables will also include the total number of events, counting multiple events per patient.

In the AE summary, preferred terms within each SOC will appear in alphabetical order as well as in decreasing order of total incidence.

Frequencies for deaths and hospitalizations will also be summarized by treatment group and overall.

Other safety analyses will be performed as appropriate

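### The SAE definition exempts any hospital admission for diagnostic work-up of an adverse event, so an unplanned overnight stay for a new event can be classed as nonserious

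*Protocol*

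**What the plan says.** Protocol 10.1.4 lists alternative criteria for a serious adverse event. One is that the event "Requires inpatient hospitalization or prolongation of existing hospitalization". The NOTE under that bullet gives the test: "Inpatient hospitalization is defined as 24 hours in a hospital or an overnight stay". The purpose of the stay is not part of it.

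The NOTE then takes three kinds of admission out:

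- an elective admission to treat something the subject had before taking study drug;
- "or a hospital admission for a diagnostic evaluation of an AE";
- an overnight stay arising only from transport, organization or accommodation, with no medical background.

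For the first two, the NOTE says the admission does not "qualify the condition or event as an SAE". The other criteria (death, threat to life, disability, congenital anomaly, important medical event) stand beside the hospitalization criterion. The last of these is left to medical and scientific judgment.

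SAEs go to the sponsor's recipient within 24 hours (Protocol 10.2.6.1). For the rest, Protocol 10.2.6.3 says "Axsome will review nonserious AEs that are recorded in the CRFs on a regular basis". Section 11 states "No Data Safety Monitoring Board will be convened during the study", and section 10.3.1 defines no adverse events of special interest. SAP 10.2 plans an SAE table by system organ class and preferred term, and adds: "Frequencies for deaths and hospitalizations will also be summarized by treatment group and overall".

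**The concern.** The hospitalization criterion turns on length of stay so that sites need not decide why a subject was kept in. The second exemption brings that question back, and answers it by removing the event. As written it covers a subject admitted overnight, unplanned, to find the cause of a new event that began on study drug. That stay meets the NOTE's own definition of inpatient hospitalization.

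Safety and tolerability are the protocol's only objective. With no data safety monitoring board and no events of special interest, the 24-hour SAE report is the only expedited route from site to sponsor that the protocol gives an ordinary adverse event (pregnancy and overdose have their own routes in 10.3.2 and 10.3.3). Whether an event is called serious also decides which tables it enters. A definition that can turn on the stated reason for admission therefore affects both timely oversight and the SAE counts by arm.

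**Working it through.** There is no planned figure to reproduce. The check sets the definition against the rules that depend on it; the only arithmetic is a count of days.

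**Step 1. Does the wording limit the exemption?** The qualifiers for an elective admission and a pre-existing condition belong to the first exemption. The second starts afresh with its own noun and concerns an adverse event. It sets no condition on urgency, duration or result. The third exemption does carry a limit (no medical background), so the NOTE states limits elsewhere but none here.

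**Step 2. How are admissions of 24 hours or overnight classified?**

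| Reason for admission | Hospitalization criterion | Outcome |
|---|---|---|
| Treatment of the event | Met | SAE |
| Work-up only; event is fatal, life-threatening or disabling | Exempted | SAE by another criterion |
| Work-up only; event might be an important medical event | Exempted | SAE only if the investigator so judges |
| Work-up only; no other criterion | Exempted | Not an SAE |
| Both work-up and treatment | No rule given | Unclear |

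The concern lies in the last three rows.

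**Step 3. What depends on the classification?**

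- Report to the sponsor: 24 hours for an SAE (Protocol 10.2.6.1); otherwise regular review with no stated deadline (10.2.6.3).
- Report to authorities, if drug-related: immediate for a serious reaction, after study completion for a nonserious one (10.2.6.2).
- Return to the site with blood and urine samples for drug concentrations: prompted by a serious event (10.2.4).
- Screen failures: only serious events are collected (10.2), so an exempted event in a screen failure leaves no record.
- Outputs: the SAE listing (Protocol 12.4.3.1) and SAE table (SAP 10.2).

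**Step 4. Tabulation windows.** These also split by seriousness.

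- *Protocol 12.4.3.1:* nonserious events count to 7 days after last dose, serious ones to 30. Difference: 30 − 7 = 23 days (days 8 to 30).
- *SAP 10.2:* nonserious events are tabulated if onset is before the date of last dose, serious ones if onset is before the final visit plus 30 days. Assume last dose on Day 42 and visits on their nominal days. The last nonserious onset tabulated is then Day 41.
  - Final visit is Visit 9 (Day 49): 49 + 30 = 79, so serious onsets count to Day 78. Gap: 78 − 42 + 1 = 37 days.
  - Final visit is Visit 8 (Day 42): 42 + 30 = 72, so to Day 71. Gap: 71 − 42 + 1 = 30 days.
- *Protocol 10.1.5:* treatment-emergent means onset up to 30 days after the last study visit, whatever the seriousness. Gap: none.

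In the first two windows a late exempted event leaves the TEAE summary tables as well as the SAE table. The SAP still lists every recorded adverse event.

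**Step 5. How many events?** Neither document gives a rate of admissions, or of admissions for work-up. The count cannot be estimated.

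**The case against.** The best defence is that the sentence is a note scoping its own bullet. On that view there is no clash between sections: admission for work-up simply does not confer seriousness by itself, and an event can still qualify under any other criterion. The first half is right. This is a carve-out inside one criterion, and calling it a contradiction between parts of the protocol would overstate it. The second half is a fair reading, but it leaves the important-medical-event criterion as the main net. That net depends on judgment, exercised by an investigator who has just read that such an admission does not qualify the event.

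Four stronger readings are tempting and not supported:

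- *A convulsion managed at home is serious but one admitted for work-up is not.* The protocol lists "blood dyscrasias or convulsions that do not result in hospitalization" as an example of an important medical event. An admitted convulsion can qualify by the same judgment; it just falls outside the wording of the example.
- *A late exempted event is not treatment-emergent at all.* This holds only under Protocol 12.4.3.1. Under Protocol 10.1.5 it is a TEAE for 30 days after the last visit, and the SAP's definition has no end date; the SAP restricts only what is tabulated.
- *The SAE rate is understated by a set number of percentage points.* Any such figure needs an admission count the documents do not give. The planned 30 per arm are compliant completers, whereas SAEs are counted in everyone dosed.
- *The SAE and hospitalization tables will disagree.* They may. The SAP names no source for hospitalizations. If the source is the CRF seriousness item, which gives hospitalization as an example (Protocol 10.2.3), both could miss the event. If it is all admissions, the hospitalization summary would show it.

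Nor do the documents say what share of unplanned admissions start as diagnostic work-up, so the exemption's practical reach is unknown. A separate Safety Management Plan holds further reporting detail (Protocol 10.2.6.1) and was not available; it might narrow the clause in practice.

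**Conclusion.** The concern holds as an over-broad exemption. A site following Protocol 10.1.4 could class an unplanned overnight admission for a new adverse event as nonserious because its purpose was diagnostic. The effect is confined to admissions for work-up where no other criterion is met, or where only investigator judgment brings the event back. Mixed admissions are left undecided. Treatment admissions are unaffected, and in randomized subjects nothing exempted is lost from the adverse event record.

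The consequences that can be stated are the loss of the 24-hour deadline, delayed reporting of related events to authorities, absence from SAE outputs, and non-collection in screen failures. The possible loss of late events from TEAE tables (23 days under Protocol 12.4.3.1; 37 or 30 days under SAP 10.2 with last dose on Day 42) depends on which of the documents' windows is applied. The number of events is unknown and could be zero. The clause should still be corrected, because it weakens the main expedited safety route in a study without a monitoring board, and the correction is small.

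**What to change.** Delete "or a hospital admission for a diagnostic evaluation of an AE" from the NOTE in Protocol 10.1.4. The elective-admission clause already covers pre-existing conditions, so no replacement wording is needed. An adverse event requiring an inpatient stay of 24 hours or overnight is then serious, as the criterion itself says.

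In SAP 10.2, use the same definition for the SAE table and the hospitalization summary, and name the data source for the latter so that the two can be reconciled. The differing TEAE windows in Protocol 10.1.5, Protocol 12.4.3.1 and SAP 10.2 should be reconciled at the same time; that inconsistency would remain even after the clause is removed.

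The cost is one clause in a protocol amendment, a memo to sites and a short SAP edit. The downside is a few additional SAE forms, some for events that prove benign.

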10.1.5 Treatment-Emergent Adverse Events

An AE is defined as treatment emergent if the first onset or worsening is after the first administration of the study drug and not more than 30 days after the last study visit.

10.2 Management of Adverse Events

Adverse events will be collected from the time of signing the ICF through 30 days after the last study visit or Early Termination, whichever occurs first. Only Serious adverse events will be collected for subjects who screen fail.

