All study drug including AXS-05 tablets and bupropion SR tablets are of identical appearance and similar weight in order to maintain the integrity of the blind.

Assessments and Visits

Study visits will occur at Visit 1, Baseline (Day 0, Visit 2), and on Days 3, 7, 14, 21, 28, 42 and 49 (Visits 3 - 9). Study procedures and assessments will be performed during study visits as outlined in the Schedule of Assessments (See Section 17.2). Visit 3 (Day 3) will be conducted telephonically. Subjects will be reminded during Visit 3 to begin BID dosing on Day 4. All subjects completing 6 weeks of treatment or subjects prematurely discontinuing from the study will be required to complete a follow-up visit one week after the last dose of study drug (Visit 9), telephonically.

Assessments will include safety parameters, MADRS, QIDS-SR-16, CGI-S and CGI-I.

Study drug compliance will also be assessed at the 80% level by counting the number of tablets dispensed and returned. Non-compliant subjects are subject to early termination from the study and should return for an Early Termination visit.

Safety will be assessed by evaluating treatment-emergent AEs (TEAEs); clinical laboratory test results; vital sign measurements; and physical examination findings.

All AEs observed by the study personnel or reported by the subject during the study (from the time of the signing of the informed consent form [ICF] through follow up) will be documented.

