8.11 Treatment Compliance

Study drug compliance will be closely monitored by counting the number of tablets dispensed and returned ______.

Subjects will be instructed to bring any unused study drug and empty containers to the clinic on Days 7, 14, 21, 28 and 42 (Visits 4-8), or at the time of early study discontinuation. Before new study drug is dispensed at each visit, every effort will be made to collect the unused study drug to confirm compliance. Investigators will perform drug accountability of study drug at each visit to determine a subject's usage. Study drug compliance will be assessed at the 80% level.

If non-compliance is determined, the site will be notified in writing and noncompliant subjects may be discontinued from the study. Discontinued subjects should return for an Early Termination visit, performing all the study assessments for Visit 8/ET and then complete the follow-up visit one week after the final dose of study drug (Visit 9).

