10.3.2 Pregnancy

In the rare chance that a pregnancy occurs or is suspected, women should be instructed to contact the Investigator or study staff immediately.

A woman who becomes pregnant during study drug treatment or within 30 days of discontinuing the study drug will be immediately discontinued from study participation. The Investigator must report the pregnancy as if it were an SAE within 24 hours of learning of the pregnancy. The Investigator should contact the designated individual(s) who receive SAE notification and record information related to the pregnancy on a Pregnancy and Lactation Exposure Form/other designated form provided by Axsome or its designee.

Early termination visit assessments are required as soon as possible after learning of the pregnancy. The Investigator is also responsible for following the pregnancy until delivery or termination. Findings must be reported on the Pregnancy and Lactation Exposure Form/other designated form and forwarded to the designated individual(s). The event meets the SAE criterion only if it results in a spontaneous abortion or a congenital anomaly. If the pregnancy is associated with an SAE (e.g., if the mother is hospitalized for hemorrhage), a separate SAE Form must be filed with the appropriate serious criterion (e.g., hospitalization) indicated in addition to the aforementioned designated form.

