12.4.3.1 Adverse Events

Adverse events will be coded by system organ class (SOC) and preferred term using the Medical Dictionary for Regulatory Activities reporting system. Treatment-emergent AEs are defined as any of the following:

- Non-serious AEs with onset on the date of first dose of treatment with the study drug through follow up (7 days after the last dose of study drug);
- Serious AEs with onset on the date of first dose of treatment with the study drug through 30 days after the last dose of study drug;

The number and percentage of subjects with TEAEs will be displayed for each treatment group by SOC and preferred term. Additionally, TEAEs will be tabulated for each treatment group by severity and by relationship to the study drug. A listing of SAEs will be provided if applicable.

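### The protocol and SAP give conflicting end dates for collecting and counting adverse events, and about 23 of the 30 days in the post-dose SAE window rest on passive reporting

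*Protocol*

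**What the plan says.** **When collection ends**

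- Protocol 6.1 documents AEs "from the time of the signing of the informed consent form [ICF] through follow up". Follow-up is the Visit 9 telephone call, one week after the last dose.
- Protocol 10.2 collects AEs from consent "through 30 days after the last study visit or Early Termination, whichever occurs first". Protocol 10.2.3 names Section 10.2 as the place where the period of observation is defined.

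**Which events count**

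- Protocol 10.1.5 treats any AE as treatment-emergent if its onset or worsening follows the first dose and is "not more than 30 days after the last study visit".
- Protocol 12.4.3.1 ends the non-serious window 7 days after the last dose. Serious events count "through 30 days after the last dose of study drug".
- SAP 10.2 tabulates non-serious events with onset before the date of last dose, and serious events with onset before the final visit plus 30 days.
- Protocol 10.3.2 covers "A woman who becomes pregnant during study drug treatment or within 30 days of discontinuing the study drug".

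**When subjects are contacted**

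- Protocol 6.1, 8.11 and 9.1.6 place the Visit 9 call one week after the last dose for completers and for subjects who stop early. It includes an AE review and the C-SSRS.
- The Schedule of Assessments (17.2) has nothing after Visit 9 (Day 49, plus or minus 2).
- The last pregnancy test is at Visit 8/ET (9.3.3.2.2).

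**The concern.** The rule that decides what enters the database and the rules that decide what is tabulated do not share an end date or an anchor. Some count from the last dose and some from the last visit. The clause about Early Termination can be read in two ways that differ by 30 days for the same subject.

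A site that works from 6.1 may stop recording at the Visit 9 call, while a site that works from 10.2 continues for about a month. Detection under 10.2.1 rests on questions asked at visits, and there are none after Visit 9. An SAE table with a window of 30 days after the last dose would then look complete although most of that window was never actively asked about.

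This matters here because safety and tolerability is the only objective in Protocol Section 5, no data safety monitoring board is convened (Section 11), and about 30 completers per arm are planned (12.2). With groups of that size, one or two late SAEs that are captured or missed can change the by-arm picture.

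**Working it through.** **Inputs.** Last dose on Day 42 and Visit 9 on Day 49 plus or minus 2 (6.1, 17.2). SAE window of 30 days after the last dose (12.4.3.1). 60 planned completers (12.2). Assumption: the last or final visit means Visit 9.

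**Step 1: the plan's own timeline.** 42 + 7 = Day 49, and 4 + 6 + 1 = 11 weeks. Both agree with the protocol (6.1 and 9.2).

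**Step 2: end points for a completer.**

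| Rule | Calculation | Ends on Day | Days after last dose |
|---|---|---|---|
| Protocol 6.1, collection | Visit 9 | 49 | 7 |
| Protocol 10.2, collection | 49 + 30 | 79 | 37 |
| Protocol 10.1.5, all AEs | 49 + 30 | 79 | 37 |
| Protocol 12.4.3.1, non-serious | 42 + 7 | 49 | 7 |
| Protocol 12.4.3.1, serious | 42 + 30 | 72 | 30 |
| SAP 10.2, non-serious | onset before last dose | before 42 | none |
| SAP 10.2, serious | 49 + 30 | 79 | 37 |
| Protocol 10.3.2, pregnancy | 42 + 30 | 72 | 30 |

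The two collection rules differ by 79 − 49 = 30 days. Protocol 6.1 ends 72 − 49 = 23 days before the 12.4.3.1 SAE window closes. Protocol 10.2 ends 79 − 72 = 7 days after it, so for completers 10.2 covers the whole window. If the last visit meant Visit 8, which 9.3.3.3.2 calls the final on-site visit, the Day 79 entries would become 42 + 30 = Day 72.

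**Step 3: an early terminator whose ET visit is on the day of last dose, L.**

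- Reading A, 30 days after ET: collection ends at L + 30 and covers 30 of the 30 days. That is still 37 − 30 = 7 days less than a completer gets.
- Reading B, ET itself ends collection: it ends at L and covers 0 of the 30 days. It would close before the Visit 9 AE review and C-SSRS that 8.11 and 9.1.6 ask of the same subject, so it conflicts with the schedule.

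**Step 4: days without scheduled contact.** With g the days from last dose to Visit 9, the share is (30 − g) / 30.

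- g = 7: 23 of 30 days, 77%.
- g = 5 to 9 (Visit 9 window, last dose on Day 42): 25 to 21 days, 83% to 70%.
- g = 3 to 11 (assuming last dose moves with the Visit 8 window, independently of Visit 9): 27 to 19 days, 90% to 63%.
- Counted to last visit + 30 days: 30 of 37 days, 81%.
- For 60 completers at g = 7: 60 × 23 = 1,380 of 60 × 30 = 1,800 person-days.

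**Step 5: what remains after Visit 9.**

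- SAEs are reported within 24 hours once the site learns of them (10.2.6.1).
- Suspected serious drug reactions are reportable without time limit (10.2.6.2).
- Women are to be told to contact the site about a pregnancy (10.3.2).
- An in-clinic visit is possible if needed (9.1.6).
- Known events are followed up (10.2.5).

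None of these is a scheduled enquiry about new events. Once the observation period closes, only 10.2.6.2 is expressly without a time limit, and it covers only serious events suspected to be drug-related.

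**The case against.** The strongest reply is that 10.2 governs. Section 10.2.3 points to it, 6.1 is only a design overview, and for completers 10.2 outlasts the SAE window. The natural reading of the ET clause is 30 days after ET, which also covers the window. Passive reporting after a last call is a legitimate choice in a small Phase 2 trial. Most of this stands. It reduces the conflict between 6.1 and 10.2 to one that alignment resolves. It does not settle the ET wording, the difference between last-dose and last-visit anchors, or the absence of any stated method of ascertainment after Visit 9.

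A reader might infer three stronger things, which the documents do not support:

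- **That most of the window is unobserved.** It lacks scheduled contact, but reporting routes stay open. Under-ascertainment is possible; total loss is not shown.
- **That early terminators have no follow-up.** This needs Reading B, which contradicts the Visit 9 requirements. Subjects who stop drug are also encouraged to keep attending visits (7.3).
- **That the SAE comparison favours the arm with more dropout.** This needs unequal discontinuation and unequal capture. The documents give no dropout rate, no split of reasons and no expected SAE count. Protocol 12.4.3 plans no formal safety comparison, and SAP 10.0 treats any as post hoc.

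**Conclusion.** The point holds as a conflict between end points combined with unscheduled ascertainment. For a completer, the end points that reach the last dose or beyond fall on about Day 49, Day 72 or Day 79 according to section. For an early terminator, 10.2 has two readings 30 days apart, one of them hard to square with the schedule. About 23 of the 30 post-dose days (77%; 21 to 25 days over the Visit 9 window) rely on passive reporting. Late SAEs and pregnancies may therefore be under-ascertained, and unevenly so if sites apply different sections.

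This rests on a last dose on Day 42 and on Visit 9 being the last visit. How many events would be missed, and in which arm, cannot be derived from the documents. The inconsistency should be corrected because it decides which SAEs reach the database and the correction is cheap. It does not invalidate the safety analysis.

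**What to change.** 1. **One end of collection.** Remove the Early Termination alternative and the whichever-is-first condition from Protocol 10.2. State one end of collection per event type, the same for completers and early terminators. It should never be shorter than the SAE counting window, so at least 30 days after the last dose for SAEs and pregnancies. Then align Protocol 6.1, 10.1.5, 12.4.3.1 and SAP 10.2, including the SAP's earlier cut-off for non-serious events. Changing only 6.1 and 10.2 would leave new conflicts with 10.1.5 and the SAP. Choosing exactly 30 days after the last dose would shorten completers' collection under 10.2 from about Day 79 to Day 72, so that choice should be made knowingly.
2. **Visit 9 call.** Instruct subjects to report any hospitalization, serious event or pregnancy until that date.
3. **SAP presentation.** Show SAEs through Visit 9, which are actively ascertained, separately from later SAEs, labelled as spontaneously reported.

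The cost is wording in five sections (through a protocol amendment and a SAP revision before database lock), one line in the call script, one table footnote, and possibly a few more late SAE reports. No visit or procedure is added, so the 23 days remain without scheduled contact. The gain is a uniform rule, a prompt to report, and a table that says how its events were found.
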